RWE23-SAF-001:Comparative safety study to assess the risk of AL of 2-row vs 3-row circular staplers

1. LIST OF ABBREVIATIONS

Abbreviation	Definition
AL	Anastomotic Leak
ASD	Absolute Standardized Difference
CCI	Charlson Comorbidity Index
CHU	Complaint Handling Unit
CI	Confidence Interval
ICD	International Classification of Disease
PCS	Procedure Coding System
PHD	Premier Healthcare Database
PSW	Propensity Score Weighting
RR	Relative Risk
RWD	Real World Data
SD	Standard Deviation
US	United States

3. MAJOR AMENDMENTS

Revision Number	Date	Section of study protocol	Amendment or update	Reason
1	January 06, 2023		Original	

4. RATIONALE AND BACKGROUND

Anastomotic leak (AL) after colorectal surgery is a serious complication, and can result in intra-abdominal abscess, wound infection, bowel obstruction, rupture of the operation wound, or require reoperation.¹⁻⁴ Male sex, low anterior resection, and patient comorbidity including malnutrition, obesity (body mass index >30 kg/m²), and diabetes, are widely reported risk factors for AL.⁵⁻⁸

The use of circular stapling devices to facilitate colorectal anastomosis has been demonstrated to reduce the risk of AL vs hand sewn sutures and is widely used in colorectal anastomosis after left-sided colorectal surgery. Many circular staplers are characterized by two rows of staples fired under manual grip force, aimed to guarantee a high anastomotic resistance with reduced tissue damage. Among them are Ethicon manual circular staplers and Medtronic EEA™ Circular Stapler with DST Series™ Technology (device variants described in Table 1).

Technological advancements led to the introduction of the Tri-staple™ Technology of manual staplers in the US Market in 2018 (Medtronic EEA™ circular stapler with Tri-Staple™ technology), which includes three staple lines and is thought to guarantee a higher resistance of the anastomotic site with less stress on tissue as compared to the two-row circular staplers.⁹⁻¹¹ Based on the results of two 2022 publications, 2-row manual circular staplers, including Ethicon manual circular staplers and Medtronic EEA™ Circular Stapler with DST Series™ Technology, may have a higher risk of AL, when compared to the Medtronic EEA™ circular stapler with Tri-Staple™ technology (3-row manual circular staplers).^{8, 12} This evidence was reported from single-center retrospective studies conducted in Italy and Japan. Such settings have the potential for selection bias, and the estimates of AL risks are limited by the small sample size included in both studies and the variations in the diagnosis consensus to ascertain AL cases. A comparative analysis of the risk of AL among two-row versus three-row manual circular staplers in colorectal anastomosis using a nationally representative database has not been fully examined or demonstrated in the United States (US).

Health-care databases can be a useful source of data for safety surveillance of medical devices. Using data from a large U.S. health-care database, the current study is designed to estimate the risk of AL among patients who underwent a left-sided colorectal surgery with use of a 2-row manual circular stapler (Ethicon Manual Circular Staplers or Medtronic EEA™ Circular Stapler with DST™ technology) relative to use of a 3-row manual circular stapler (i.e., Medtronic EEA™ Circular Stapler with Tri-Staple™ technology).

A future study to estimate the risk of AL among patients who underwent a left-sided colorectal surgery with use of a 2-row powered circular stapler (Ethicon Powered Circular Stapler) relative to use of a 3-row manual circular stapler (i.e., Medtronic EEA™ Circular Stapler with Tri-Staple™ technology) is planned. The timing of this study execution will be based on sample size of the study devices of interest accumulated in the PHD and appropriate statistical power.

RWE23-SAF-001:Comparative safety study to assess the risk of AL of 2-row vs 3-row circular staplers

Table 1: Circular Staplers

Variant	Description / Image	Product Code
1) Ethicon Manual 2-row Circular Staplers		
Curved Circular Staplers	Legacy Curved Intraluminal Stapler (ILS) 	CDH21A CDH25A CDH29A CDH33A
	Ethicon Circular Stapler* (not available in US) 	CDH21B* CDH25B* CDH29B* CDH33B*
Endoscopic Circular Staplers	Legacy Endoscopic Intraluminal Stapler (ILS) 	ECS21A ECS25A ECS29A ECS33A
	Ethicon Circular Stapler, XL Sealed 	ECS21B ECS25B ECS29B ECS33B
2) Medtronic EEA™ Circular Stapler		
Medtronic EEA™ Circular Stapler with DST Series™ Technology (2-row)		EEA2135 EEA21 EEAXL2135 EEAXL21 EEA2535 EEA25 EEAXL2535 EEAXL25 EEA2835 EEA28 EEAXL2835 EEAXL28 EEA31 EEAXL31 EEA33 EEAXL33
Medtronic EEA™ Circular Stapler with Tri-Staple™ Technology (3-row)		TRIEEA28MT TRIEEA28XT TRIEEAXL28MT TRIEEAXL28XT TRIEEA31MT TRIEEA31XT TRIEEAXL31MT TRIEEAXL31XT

*Ethicon Circular Stapler with product codes of CDH21B, CDH25B, CDH29B and CDH33B are not available in the US, hence not included in this study.

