6.9.2 Primary Comparative analysis

The goals of comparative analyses are to: 1) estimate the RR of AL for Ethicon Manual Circular Staplers compared to Medtronic EEA™ Circular Stapler with Tri-Staple™ Technology; 2) estimate the RR of AL for the Medtronic EEA™ Circular Stapler with DST Series™ Technology compared to Medtronic EEA™ Circular Stapler with Tri-Staple™.

The primary analyses will be conducted separately for the comparison between Ethicon Manual Circular Stapler versus Medtronic EEA™ Circular Stapler with Tri-Staple™ Technology and the comparison between Medtronic EEA™ Circular Stapler with DST™ Technology and Medtronic EEA™ Circular Stapler with Tri-Staple™ Technology. See the expected outputs in [Table B- 7](#) and [Table B- 8](#).

A propensity score weighting (PSW) method will be used to control for potential confounders by balancing the distribution of baseline demographic, clinical, and procedural characteristics between the comparison groups. The following baseline variables will be considered in the propensity score model based on their clinical relevance to the safety of the device: patient demographics (age, sex, and race), clinical characteristics (CCI, comorbid conditions, diverting stoma occurred prior to or on the same day as the index procedure), procedural characteristics (procedure year, surgical site, primary diagnosis, surgical approach, and admission type), and hospital and provider

RWE23-SAF-001:Comparative safety study to assess the risk of AL of 2-row vs 3-row circular staplers

characteristics (hospital region, hospital location, hospital setting, hospital bed size, and surgeon specialty).

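### The 3-row comparator is listed only with 28 and 31 codes while both 2-row cohorts span 21 to 33, and the readable plan never restricts, balances or reports stapler size

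*Supplement*

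**What the plan says.** Section 4, Table 1 defines each device family by product code.

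- 3-row comparator (Tri-Staple): "TRIEEA28MT TRIEEA28XT TRIEEAXL28MT TRIEEAXL28XT TRIEEA31MT TRIEEA31XT TRIEEAXL31MT TRIEEAXL31XT".
- Ethicon curved: "CDH21A CDH25A CDH29A CDH33A". Ethicon endoscopic: "ECS21A ECS25A ECS29A ECS33A" and "ECS21B ECS25B ECS29B ECS33B".
- Medtronic DST: "EEA2135 EEA21 EEAXL2135 EEAXL21 EEA2535 EEA25 EEAXL2535 EEAXL25 EEA2835 EEA28 EEAXL2835 EEAXL28 EEA31 EEAXL31 EEA33 EEAXL33".

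The only codes set aside are the curved Ethicon codes with suffix B. The Table 1 footnote says these "are not available in the US, hence not included in this study", so the reason is availability and not size.

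Section 6.3 admits any patient billed for a study device, with no limit on size. Section 6.6 defines no size variable. Among the procedural variables, section 6.9.2 puts into the propensity model "procedural characteristics (procedure year, surgical site, primary diagnosis, surgical approach, and admission type", and its other groups of variables contain no size either. The same section weights the comparator to resemble the target group and fits an outcome model with device group as the only term. It allows extra covariates only if they are already in the propensity model and remain unbalanced. The table shells in Appendices B and C have no row for size, and section 8 does not mention it.

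**The concern.** The title and section 6.2 frame the study as 2-row against 3-row staplers, so readers will take the relative risk as the effect of row number. The families also differ in the sizes they offer. If the smaller sizes were used in the target cohorts and go with a different leak risk, part of that difference would be credited to, or hidden behind, row number.

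Nothing in the planned analysis would reveal this. The balance tables could look clean because size is not in them. Trimming could not single out these patients because the score carries no information on size. The fallback adjustment could never reach size because it covers only variables already in the score.

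**Working it through.** **Step 1. Size labels, counted from Table 1.** The first two digits of each code are read as the size. The protocol does not label them so, but the pattern is consistent across all three families.

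| Family | Codes | 21 | 25 | 28 | 29 | 31 | 33 |
|---|---|---|---|---|---|---|---|
| Ethicon (US codes) | 12 | 3 | 3 | – | 3 | – | 3 |
| DST | 16 | 4 | 4 | 4 | – | 2 | 2 |
| Tri-Staple | 8 | – | – | 4 | – | 4 | – |

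Half of the codes in each target family (6 of 12 and 8 of 16) are 21 or 25, where the comparator has none. These are shares of codes and not of patients. The comparator also has no 33 and no 29, so Ethicon and Tri-Staple share no exact size label.

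**Step 2. Possible effect on the relative risk.** Let f be the share of target patients with a 21 or 25, and s their leak risk relative to the other patients. Let row number have no effect, and let all comparator patients carry the risk p of those other patients. Then

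expected crude RR = [(1 − f)p + f·s·p] / p = 1 − f + f·s.

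The documents give neither f nor s, so both are assumed:

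| f | s = 0.5 | s = 1.5 | s = 2 |
|---|---|---|---|
| 10% | 0.95 | 1.05 | 1.10 |
| 20% | 0.90 | 1.10 | 1.20 |
| 40% | 0.80 | 1.20 | 1.40 |

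For example, f = 0.20 and s = 2 give 1 − 0.20 + 0.40 = 1.20.

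For scale, take the Table 2 sizes with 3% risk in both groups. The crude standard error of the log relative risk is √[0.97/(6,000 × 0.03) + 0.97/(500 × 0.03)] = √(0.00539 + 0.06467) = 0.265. A shift to 1.10 or 1.20 (0.095 or 0.182 on the log scale) is then about 0.36 or 0.69 of a standard error.

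**Step 3. The plan's power, and the price of restriction.** Section 6.8 states one-sided 0.025, about 6,000 target patients, and 500 comparator patients in Table 2. With p0 the comparator risk, p1 = RR × p0 and p̄ the pooled risk,

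power = Φ{[p1 − p0 − 1.96·√(p̄(1 − p̄)(1/n1 + 1/n0))] / √(p1(1 − p1)/n1 + p0(1 − p0)/n0)}.

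For RR 2 at 3%, p̄ = (360 + 15)/6,500 = 0.0577. The null standard error is 0.01085 and the alternative one 0.00822, so power = Φ[(0.03 − 0.02127)/0.00822] = Φ(1.06) = 0.856, as in Table 2. The other five rows also reproduce to within 0.001.

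With the target cohort reduced and the comparator kept at 500:

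| Target removed | n1 | RR 2, 3% | RR 2, 2% |
|---|---|---|---|
| 0% | 6,000 | 0.856 | 0.642 |
| 10% | 5,400 | 0.853 | 0.639 |
| 20% | 4,800 | 0.849 | 0.635 |
| 30% | 4,200 | 0.843 | 0.630 |
| 50% | 3,000 | 0.827 | 0.614 |

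The comparator sets the power, so losing half the target cohort costs 0.029 and 0.028. These are crude figures, like those in Table 2, and do not allow for weighting.

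**The case against.** A reader might infer that patients given a 21 or 25 had no chance of receiving the 3-row device, so that the effect in the target group is not identified for them. The documents do not support that. It requires size to be a fixed need of the patient, and no section says so. A patient given a 25 might have been given a 28 had the 3-row family been chosen. Size would then be part of the exposure, and the comparator cohort would already contain such patients. The objectives in section 5.2 compare device families, and a family's size range belongs to it. The risk factors named in section 4 do not include stapler size or bowel calibre. On the covariates that are listed, overlap may be intact.

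A reader might also infer that the relative risk is inflated. Neither the share of small sizes nor the sign of their effect is known. The share could be small: section 6.8 shows that the left-sided filter keeps at most about 60% of Ethicon patients (about 6,000 of more than 10,000), about 46% of DST (6,000 of 13,000) and 84% of Tri-Staple (526 of 623). The size mix of the analysed cohorts therefore cannot be read from the catalogue. Sex, surgical site, diagnosis, approach and diverting stoma are in the propensity model and may absorb part of any anatomical difference.

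Finally, three bullets in section 6.4 on exposure are redacted and might hold relevant detail.

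These arguments rule out a claim of certain or one-directional bias, and they weigh against replacing the primary cohort. They do not remove the gap: the listed families differ in size range, the readable plan has no means of showing whether that matters, and the study is presented as a test of row number.

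**Conclusion.** The point stands in conditional form. That the code ranges differ and that size is neither restricted, balanced nor reported follows directly from the readable text, once the digits are read as sizes. Whether this distorts the relative risk depends on two things the documents do not give: how often 21 or 25 was used in left-sided surgery, and how size relates to leak risk.

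Over the illustrated range a true relative risk of 1 could appear as 0.80 to 1.40; at a 20% share, as 0.90 to 1.20. This is before any part is absorbed by the measured covariates, and at the 20% share it is less than one crude standard error. It could create or mask a modest difference but would not by itself produce the relative risks of 2 or more for which Table 2 shows substantial power. Table 2 itself is unaffected.

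As planned, the all-sizes result supports a statement about device families, and attributing it to row number needs further evidence.

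**What to change.** 1. In section 6.6.2, define a size band derived from the product code, and report it by cohort in Tables B-2 to B-5.
2. In section 6.9.4, prespecify an analysis that repeats both comparisons with the target cohorts restricted to sizes at or next to the comparator's (28/29 and 31/33), with the size band in the propensity model. State as an assumption that 29 is treated like 28, and 33 like 31, because the comparator has neither 29 nor 33. For DST, add a version restricted to exactly 28 and 31; no such version exists for Ethicon.
3. Keep the all-sizes analysis and describe it as a comparison of device families. Attribute a difference to row number only if the size-restricted result agrees, and say so in section 8.

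Adding a size term to the all-sizes model would not be enough. No weighting of comparator patients can reproduce sizes absent from that cohort, and a regression term would extrapolate.

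The cost is protocol wording and a filter on codes already used to define exposure. The restricted result does not cover 21 and 25, and the power loss is the small one shown above.

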5. RESEARCH QUESTIONS AND OBJECTIVES

5.1 Research Question(s)

- 1) What is the risk of AL within 30 days post-index procedure where Ethicon Manual Circular Staplers, Medtronic EEA™ Circular Stapler with DST Series™ Technology, or Medtronic EEA™ Circular Stapler with Tri-Staple™ Technology were used
- 2) What is the relative risk of AL within 30 days post-index procedure, in which Ethicon Manual Circular Staplers were used, in comparison to the Medtronic EEA™ Circular Stapler with Tri-Staple™ Technology?
- 3) What is the relative risk of AL within 30 days post-index procedure, in which Medtronic EEA™ Circular Stapler with DST Series™ Technology was used, in comparison to the Medtronic EEA™ Circular Stapler with Tri-Staple™ Technology?

5.2 Objectives

Among patients who underwent a left-sided colorectal surgery (i.e., the index procedure), such as hemicolectomy, sigmoid colectomy, or rectal resection, in which a study device (Ethicon Manual Circular Staplers, Medtronic EEA™ Circular Stapler with DST Series™ Technology, or Medtronic EEA™ Circular Stapler with Tri-Staple™ Technology) was used:

5.2.1 Primary Objectives

- 1) To estimate the cumulative incidence and 95% confidence intervals (CI) of AL within 30 days post-index procedure stratified by study device, and by patient characteristics (including demographic, clinical, procedural, hospital, and provider characteristics).
- 2) To estimate the unadjusted and adjusted relative risk and 95% CIs of AL within 30 days post-index procedure for Ethicon Manual Circular Staplers compared to Medtronic EEA™ Circular Stapler with Tri-Staple™ Technology.
- 3) To estimate the unadjusted and adjusted relative risk and 95% CIs of AL within 30 days post-index procedure for Medtronic EEA™ Circular Stapler with DST Series™ Technology compared to Medtronic EEA™ Circular Stapler with Tri-Staple™ Technology.

5.2.2 Secondary Objectives

- 1) To estimate the unadjusted and adjusted relative risk and 95% CIs of AL within 30 days post-index procedure for Ethicon Manual Circular Staplers compared to Medtronic EEA™ Circular Stapler with Tri-Staple™ Technology, separately in with and without a diverting stoma prior to or on the same day as a left-sided colorectal surgery during the index admission.
- 2) To estimate the unadjusted and adjusted relative risk and 95% CIs of AL within 30 days post-index procedure for Medtronic EEA™ Circular Stapler with DST Series™ Technology compared to Medtronic EEA™ Circular Stapler with Tri-Staple™ Technology separately in with and without a diverting stoma prior to or on the same day as a left-sided colorectal surgery during the index admission.

6. RESEARCH METHODS

6.1 Data Source(s)

This study will use hospital billing records contained in the Premier Healthcare Database (PHD). The PHD contains complete clinical coding, hospital cost, and patient billing data from more than 1,041 hospitals throughout the United States (US). The PHD represents approximately 25% of inpatient hospital stays in the US, and it includes a wide variety of regions and most healthcare insurances in the US. Premier collects data from participating hospitals in its health care alliance. The Premier Alliance was formed to improve the quality of care. Participation in the Premier Alliance is voluntary. Although the database excludes federally funded hospitals (e.g., Veterans Affairs), the hospitals included are nationally representative. The database contains a date-stamped log of all billed items by cost-accounting department including medications; laboratory, diagnostic, and therapeutic services; and primary and secondary diagnoses for each patient's hospitalization. Identifier-linked enrollment files provide demographic and payor information. Detailed service level information for each hospital day is recorded; this includes details on medication and devices received.¹³

6.2 Study Design

A retrospective cohort study using electronic healthcare data will be conducted to compare the risk of AL between 2-row manual circular staplers (including Ethicon Manual Circular Stapler and Medtronic EEA™ Circular Stapler with DST Series™ Technology) and 3-row manual circular staplers (i.e., Medtronic EEA™ Circular Stapler with Tri-Staple™ Technology), among patients who underwent a left-sided colorectal surgery.

With the absence of an International Classification of Diseases, 10th Revision, Clinical Modification (ICD-10-CM) code for AL, the risks and relative risks of AL will be estimated via surrogate diagnoses which usually occur concomitantly with a leak, e.g. an abscess, peritonitis, a fistula or a post-index surgery stoma formation — a surgical treatment for severe AL.

Three study cohorts, as defined below, will be identified between January 2019 (when Medtronic EEA™ Circular Stapler with Tri-Staple™ Technology became available in the US) and June 2022 or most recent available data.

- Target cohort 1: Ethicon Manual Circular Staplers – this cohort will include patients who underwent a left-sided colorectal surgery in which the Ethicon Manual Circular Stapler was used. The product family of Ethicon Endo-Surgery (EES) Circular Staplers is comprised of four primary variants: Curved, Endoscopic, Straight, and Powered anastomotic staplers. Included in this study are two manual variants: Curved and Endoscopic Circular Staplers (see Table 1).
- Target cohort 2: Medtronic EEA™ Circular Stapler with DST Series™ Technology – this cohort will include patients who underwent a left-sided colorectal surgery in which the Medtronic EEA™ Circular Stapler with DST Series™ Technology was used (see Table 1).
- Comparison cohort: Medtronic EEA™ Circular Stapler with Tri-Staple™ Technology – this

RWE23-SAF-001:Comparative safety study to assess the risk of AL of 2-row vs 3-row circular staplers

cohort will include patients in whom Medtronic EEA™ Circular Stapler with Tri-Staple™ Technology was used during the index procedure of interest (see Table 1).

This study will include two head-to-head comparisons: Ethicon Manual Circular Stapler versus Medtronic EEA™ Circular Stapler with Tri-Staple™ Technology; and Medtronic EEA™ Circular Stapler with DST™ Technology versus Medtronic EEA™ Circular Stapler with Tri-Staple™ Technology. The index procedure will be defined as the initial procedure in which the device of interest was used. The index admission will include the time from admission to discharge. Propensity score weighting (PSW) will be used for confounding adjustment, followed by log-binomial regression for risk estimation.

Stoma creations during colorectal resection are reportedly to reduce the incidence of AL or the AL-related complications¹⁴⁻¹⁶, secondary analyses will be conducted separately in those with and without a diverting stoma procedure prior to or on the same day as the index procedure (i.e., left-sided colorectal surgery) during the index admission.

6.3 Sample Selection

Inclusion Criteria

Patients who meet all of the following criteria will be included in this study:

- 1) Billing charges for a study device (Ethicon Manual Circular Stapler, Medtronic EEA™ Circular Stapler with DST Series™ Technology, or Medtronic EEA™ Circular Stapler with Tri-Staple™ Technology) between January 1, 2019, and June 30, 2022 (or latest available data)
- 2) Undergoing a left-sided colorectal surgery (i.e., the index procedure), defined as presence of a qualifying procedure code for left-sided colorectal surgery (see [Table A-1](#))
- 3) Aged 18 years or older at the index procedure.

Exclusion Criteria

Patients who meet any of the following criteria will be excluded:

- 1) Patient encounters where more than one study device (Ethicon Manual Circular Stapler, Medtronic EEA™ Circular Stapler with DST Series™ Technology, or Medtronic EEA™ Circular Stapler with Tri-Staple™ Technology) was used in the same index procedure
- 2) Missing patient age or sex
- 3) Presence of an admission diagnosis indicating anastomotic leak (See ICD-10-CM in the [Table A-2](#)) during the index admission noted as present on admission*

*Present on admission will be identified with “Yes” in the present on admission field in the PHD.

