6.8 Sample Size and Study Power

A feasibility analysis identified more than 10,000 patients in PHD between 2019 and 2021 who were treated surgically with the use of Ethicon Manual Circular Stapler. Among those, approximately 6,000 patients had a left-sided colorectal surgery.

Among approximately 13,000 patients who were treated surgically with Medtronic EEA™ Circular Stapler with DST Series™ Technology, about 6,000 patients had a left-sided colorectal surgery in the PHD.

A similar analysis identified 623 patients in PHD between 2019 and 2021 who underwent surgical procedures where Medtronic EEA™ Circular Stapler with Tri-Staple™ Technology was used. Among those, 526 underwent a left-sided colorectal surgery.

The final sample sizes for the study will vary based on applying the inclusion and exclusion criteria, as well as additional data beyond 2021 being available from PHD.

Power estimates assuming different combinations of relative risk, sample size, and the cumulative incidence of AL in the comparison cohort—Medtronic EEA™ Circular Stapler with Tri-Staple™ Technology— are provided in [Table 2](#)

[Table 2.](#) The calculations assumed one-sided tests at a significance level of 0.025 (or type I error of 0.025). The estimated cumulative incidence of AL among patients who underwent a colorectal surgery with the use of Medtronic EEA™ Circular Stapler with Tri-Staple™ Technology ranges from 2% to 3.5% in the literature.^{8,12}

[Table 2: Power estimation, by relative risk](#)

Relative Risk	AL risk in the comparison cohort	Sample size in the target cohort	Sample size in the comparison cohort	Power
2.5	3%	6,000	500	0.995
2	3%	6,000	500	0.856
1.5	3%	6,000	500	0.324
2.5	2%	6,000	500	0.938
2	2%	6,000	500	0.642
1.5	2%	6,000	500	0.209

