The weighting will be carried out for the comparator group to make it comparable in propensity score to the target group. Two propensity score weighting methods— untrimmed and trimmed— can be used to balance the data to make the target group and the comparison group comparable on the measured confounders. The choice among the methods will be based on which provided the best balance. Propensity score methods that estimate the average treatment effect on the treated will be calculated and will be compared on the basis of covariate balance as measured by the absolute standardized difference (ASD), which is the difference in means or proportions expressed in pooled standard deviation units. We will compare the approaches on the basis of the number of variables with an ASD of >0.10 and the mean ASD, and the weighting approach with the fewest number of variables with covariate imbalance will be selected for analysis. If two methods achieve the same minimum number of variables with covariate imbalance, the method with the smallest ASD across all variables will be selected for outcome analysis. Notably, one data analyst will balance the data without access to the outcome data and a separate individual will perform the outcome analysis using the balanced data, thus removing the potential for bias resulting from repeated applications of covariate balancing to obtain a desired study outcome.

In the final PSW cohorts, covariate balanced cumulative incidences and 95% CI will be calculated for all device cohorts. A weighted (covariate balance weights) log-binomial regression outcome will be used with treatment as the only explanatory variable to estimate the covariate balanced RR (target group versus the comparator group for the study outcome of interest). A cluster robust standard error approach will be applied to calculate the variability in the estimate and to construct two-sided 95% confidence intervals. All variables included in the propensity score model are prespecified confounders of the relationship between the circular stapler and AL. If any of those variable don't balance well through propensity scores, it will be added as a covariate in the log-binomial regression model.

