APPENDIX A: DIAGOSIS AND PROCEDURE CODES

Table A- 1: Procedure Codes (ICD-10-PCS) for Left-sided Colorectal Surgery

CODE	CODE DESCRIPTION
ODTG%	Resection, large intestine, left
ODTM%	Resection, Descending Colon
ODTN%	Resection, Sigmoid Colon
ODTP%	Resection, Rectum
ODBG%	Excision, large intestine, left
ODBM%	Excision, Descending Colon
ODBN%	Excision, Sigmoid Colon
ODBP%	Excision, Rectum
ODQM%	Repair, Descending Colon
ODQN%	Repair, Sigmoid Colon
ODQP%	Repair, Rectum

'%' at the end of the code denotes any value for subsequent characters.

'%' in the middle of the code denotes any valid value for a character in that specific position

RWE23-SAF-001:Comparative safety study to assess the risk of AL of 2-row vs 3-row circular staplers

Table A- 2: Diagnosis Codes (ICD-10-CM) Indicating Anastomotic Leak

CODE	CODE DESCRIPTION
K63.2	Fistula of intestine
K65.0	Generalized Peritonitis
K65.1	Peritoneal abscess
K91.89	Other postprocedural complications and disorders of digestive system
Y83.2	Surgical operation with anastomosis, bypass or graft as the cause of abnormal reaction of the patient, or of later complication, without mention of misadventure at the time of the procedure

Table A- 3: Procedure Codes (ICD-10-PCS) for Diverting Stoma

CODE	CODE DESCRIPTION
0D18%%4	Bypass Small Intestine to Cutaneous
0D1B%%4	Bypass Ileum to Cutaneous
0D1E%%4	Bypass large intestine to Cutaneous
0D1H%%4	Bypass Cecum to Cutaneous
0D1K%%4	Bypass Ascending Colon to Cutaneous,
0D1L%%4	Bypass Transverse Colon to Cutaneous
0D1M%%4	Bypass Descending Colon to Cutaneous
0D1N%%4	Bypass Sigmoid Colon to Cutaneous

'%' in the middle of the code denotes any valid value for a character in that specific position

RWE23-SAF-001:Comparative safety study to assess the risk of AL of 2-row vs 3-row circular staplers

Table A- 4: Diagnosis Codes (ICD-10-CM) for Comorbid Conditions

Comorbid conditions	CODE	DESCRIPTION
Alcohol dependency	F10.2%	Alcohol dependence
Cardiovascular diseases	G45%, G46%, I60%, I61%, I62%, I63%, , I65%, I66%, I67%, I68%, I69%, H34.0%	cerebrovascular disease
	I43, I50%, I09.9, I11.0, I13.0, I13.2, I42.0, I42.5, I42.6, I42.7, I42.8, I42.9	congestive heart failure
	I20%, I23%, I24%, I25%	ischemic heart disease
	I21%, I22%	myocardial infarction
	I70%, I71%, I73.1, I73.8%, I73.9, I77.1, Z95.8%, Z95.9	peripheral artery disease
Chronic obstructive pulmonary disease	J44.0, J44.1, J44.9	Chronic obstructive pulmonary disease

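### Concurrent resection elsewhere in the bowel is neither excluded nor adjusted for, and the leak codes name no site; the likely bias is small but cheap to check

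*Supplement*

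**What the plan says.** **Who enters.** Section 6.3 asks for a study-device charge, age 18 or over, and "Undergoing a left-sided colorectal surgery (i.e., the index procedure), defined as presence of a qualifying procedure code for left-sided colorectal surgery". One Table A-1 code is enough, whatever other procedures are coded. The attrition table (B-1) adds only that surgery and device charge fall in the same admission.

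**Who is removed.** The three exclusions in 6.3 cover more than one study device in the index procedure, missing age or sex, and a leak diagnosis present on admission. None refers to a further bowel resection or a further join.

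**What is adjusted for.** Section 6.9.2 lists "procedural characteristics (procedure year, surgical site, primary diagnosis, surgical approach, and admission type", together with demographics, comorbidity, diverting stoma, and hospital and surgeon variables. Section 6.6.2 defines surgical site as a single organ taken from the primary procedure code.

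**What counts as an event.** Under 6.5, an event is any Table A-2 diagnosis in the index admission or in a readmission within 30 days, or a stoma procedure on days 1-30. Table A-2 contains "Fistula of intestine", generalized peritonitis, peritoneal abscess and two broader codes (K91.89, Y83.2). None says which anastomosis failed. The stoma codes record where the stoma was made, not where the leak arose.

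**What is checked.** The secondary analysis (6.9.3) splits on diverting stoma, and the sensitivity analysis (6.9.4) restricts on hospital enrolment. Section 8 does not mention a second anastomosis.

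**The concern.** The study compares devices on leaks at the circular-stapled join. A patient who also has, say, a small-bowel or right-colon segment removed may carry a hand-sewn or linear-stapled join as well. A leak there produces the same codes. Two consequences follow.

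- **Dilution.** Events unrelated to the study device are added to both cohorts and pull an RR above 1 toward 1. The study was prompted by reports of higher leak risk with 2-row staplers, so this error works against finding what it looks for.
- **Confounding.** If such operations are commoner with one device, the difference is not removed by weighting on any variable that measures it. This applies even where there is only one join, because a wider operation may carry more risk of abscess or peritonitis.

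**Working it through.** **1. The plan's own figures.** For Table 2, "The calculations assumed one-sided tests at a significance level of 0.025 (or type I error of 0.025". Inputs are 6,000 target patients, 500 comparators and a comparator risk of 2% or 3%. The pooled-variance normal approximation at RR 2 and 3% gives:

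- pooled risk = (15 + 360)/6,500 = 0.0577, so the SE under the null = √(0.0577 × 0.9423 × (1/500 + 1/6,000)) = 0.01085
- SE under the alternative = √(0.03 × 0.97/500 + 0.06 × 0.94/6,000) = 0.00822
- power = Φ((0.03 − 1.96 × 0.01085)/0.00822) = Φ(1.06) = 0.856, as printed

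All six rows reproduce to three decimals. Table 2 is not at fault.

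**2. Assumptions.** Neither of the following is in the documents.

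- *s*, the share of patients with a second join not made by the study device: 5-10%
- *q*, its added leak risk: 3-5%

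The comparator baseline is the plan's 3%; its literature figure "ranges from 2% to 3.5% in the literature".

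**3. Dilution, equal share in both cohorts.** Observed RR = (RR × p + s·q)/(p + s·q), with p the baseline risk.

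| True RR | p | s = 5%, q = 3% | s = 10%, q = 5% |
|---|---|---|---|
| 2.0 | 3% | 0.0615/0.0315 = 1.95 | 0.0650/0.0350 = 1.86 |
| 1.5 | 3% | 0.0465/0.0315 = 1.48 | 0.0500/0.0350 = 1.43 |
| 2.0 | 2% | 0.0415/0.0215 = 1.93 | 0.0450/0.0250 = 1.80 |
| 2.0 | 3.5% | 0.0715/0.0365 = 1.96 | 0.0750/0.0400 = 1.88 |

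Counting a patient only once if both joins leak, r + (1 − r)·s·q with r the circular-stapler leak risk, leaves 1.95 and 1.86 unchanged. A deliberately extreme 15% share with 10% leak risk gives 1.66.

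**4. Imbalance, true RR 1.0, baseline 3%.** Observed RR = (0.03 + s₁q)/(0.03 + s₀q), with s₁ the share in the target cohort and s₀ the share in the comparator.

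- 8% vs 5%, q = 3%: 0.0324/0.0315 = 1.03; reversed, 0.97
- 10% vs 5%, q = 5%: 0.0350/0.0325 = 1.08; reversed, 0.93

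**5. Set against the precision available.** Section 6.9.2 will "construct two-sided 95% confidence intervals". Before weighting, with 15 comparator events in 500:

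- RR 2.0 (360 target events): SE of log RR = √(1/360 − 1/6,000 + 1/15 − 1/500) = 0.259, interval 1.20-3.33
- RR 1.0 (180 target events): SE = √(1/180 − 1/6,000 + 1/15 − 1/500) = 0.265, interval 0.60-1.68

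Weighting the comparator would be expected to widen both. The added events are 500 × 0.0015 to 500 × 0.005, or 0.75 to 2.5 comparator events on top of 15.

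**6. Effect on power (RR 2, baseline 3%; plan 0.856).**

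| Share | Patients kept, diluted (q = 3% / 5%) | Patients excluded |
|---|---|---|
| 5% | 0.843 / 0.834 | 0.834 (475 vs 5,700) |
| 10% | 0.829 / 0.812 | 0.809 (450 vs 5,400) |

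Exclusion removes the bias but gains no power.

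**The case against.** The strongest reply is that a resection code records tissue removed, not joins made. A transverse plus descending colectomy can end in one circular-stapled anastomosis. A reader might infer that every extra resection code means a second anastomosis outside the study device; the documents do not support that, and a flag built on that reading would exclude patients whose only join is the one under study. This stands, and it limits how the flag should be defined.

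The magnitude is assumed throughout and is small beside the interval. That also stands.

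A reader might also infer that the confounding is established. Section 6.8 does show different use patterns: left-sided surgery makes up about 60% of Ethicon use (6,000 of just over 10,000), 46% of DST use (6,000/13,000) and 84% of Tri-Staple use (526/623). Those ratios describe device use before the cohort is restricted to left-sided surgery. They say nothing about second resections within it.

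The plan has partial controls. Diagnosis, approach, admission type, comorbidity, stoma and surgeon specialty are plausible correlates. The present-on-admission exclusion may remove some multi-segment cases, the multi-device exclusion catches a join made with a second study device, and the 'others' level of surgical site may catch a primary code elsewhere. None flags a hand-sewn or linear-stapled second join when the primary code is left-sided.

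Finally, 6.5 and section 8 already disclose that the outcome rests on surrogate codes, and K91.89 and Y83.2 are broader sources of non-specific events. That is true, and this point does not address them. But the section 8 statement that misclassification should be non-differential is an assumption, and non-differential false positives still dilute an RR.

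**Conclusion.** The gap is plain on the face of the plan: entry on one left-sided code, no exclusion or covariate for concurrent resection elsewhere, and an outcome that cannot locate the leak. It justifies a modest change. It does not show that the planned RR is materially wrong.

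The size in the working rests on an assumed 5-10% share, 3-5% added leak risk and 3% baseline. On those terms the RR moves by a few hundredths to about 0.14. Imbalance could push it either way, and nothing in the documents shows that imbalance exists. Neither the stoma split nor the enrolment restriction would reveal the problem if it were larger.

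**What to change.** Before outcomes are analysed:

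1. Prespecify a binary flag, concurrent non-contiguous bowel resection, from ICD-10-PCS excision or resection codes dated on the index day for small bowel, cecum, ascending colon or transverse colon. State a rule that leaves out contiguous extended resections that plausibly share one join. Restricting to the index day keeps later reoperations out of the flag.
2. Add the flag to the propensity score and balance tables, described as a marker of surgical extent or a possible second join. This deals with imbalance between devices and shows how common such cases are in each cohort.
3. Add one sensitivity row to Tables B-7 and B-8 excluding flagged patients. This deals with dilution, which balancing alone cannot.
4. Add a sentence to section 8 saying that the outcome codes do not identify the leaking anastomosis.

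The cost is one code list, one covariate and one row per table. The primary cohort keeps its size. Only the sensitivity run loses comparators: 25 to 50 of 500 if 5-10% are flagged, with power at RR 2 and 3% falling from 0.856 to 0.834-0.809. That row checks for bias; it does not recover power.
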